## **Section 5.0 Research Design**

- 5.1 Liver marker implantation: Under CT or ultrasound guidance, a marker will be implanted into the liver tumor in a fashion similar to liver tumor biopsy and a stent placement. Prophylactic antibiotics will be given to prevent infection. The marker position and geometry will be documented on the simulation CT scan for planning SRT.
- 5.2 SRT:
  - 5.2.1 Machine: Novalis with 6 MV photons will be used for imaging guided SRT.
  - 5.2.2 Doses: Doses of 40, 50, 60 or 70 Gy (daily doses of 8, 10, 12 or 14 Gy in 2 weeks) will be prescribed to 90% isodose line. The prescription isodose volume should encompass the entire PTV. The subjects will be divided into groups of 5

to receive escalating doses of the SRT. The first group will receive a daily dose of 10Gy (Dose Level II). The next group will be enrolled only after the first group has been observed for 4 weeks following the SRT to document any side effects. The observation period will be used for every increase in dose level. Each subject will only receive one dose level of the SRT.

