## 9.3 Data and Safety Monitoring Plan

This protocol will comply with monitoring and adverse event reporting requirements of the UNMC/Eppley Cancer Center Data Monitoring Plan. All research data will be stored in the case report forms in a locked file cabinet. These forms are available only to the investigators, his/her designee (i.e., the study coordinator), the UNMC Eppley Cancer Center Scientific Review Committee (SRC), and representatives of the Institutional Review Board at the University of Nebraska Medical Center. Any information obtained during this study which could identify the subject will be kept strictly confidential and will be identified by code numbers rather than the patient's name. The data safety plan also includes: Weekly review of all patients on study by the investigators. All adverse events will be reported to the PRMS Internal Audit Committee for audit by a clinician not involved with the clinical trial.

All patients will be closely followed for toxicity. Toxicity will be assessed using the revised NCI Common Toxicity Criteria (version 3.0) retrieved from the National Cancer Institute, Cancer Therapy Evaluation Program web site: ([ctepcancer.gov/forms/CTCAEv3.pdf](http://ctepcancer.gov/forms/CTCAEv3.pdf)). Therapy will be discontinued at any time due to the development of unacceptable toxicity. If a Grade 1 or 2 or 3 toxicity develops, the investigator may elect to continue the treatment with careful monitoring. Any grade 4 or greater toxicity according to CTCAE v3 will constitute a DLT. 1) SRT dose escalation will be stopped if 2 patients at a given dose level experience a DLT. If one patient has a DLT, then an additional five patients will be evaluated at the same dose level. 2) Implantation of a liver marker will be stopped if 2 patients experience implant-related-adverse events which do not response to medical or surgical management.

Therapy will be discontinued at any time due to the development of unacceptable toxicity. If, at any time, the data suggest a significant hazard to further dose escalation, regardless of whether the formal stopping rules are satisfied, dose escalation will be halted pending a review of all data. There will be a four week waiting period after the last patient in each cohort completes radiation therapy for toxicity evaluation between dose levels.

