#### Endpoints

Toxicity will be graded by NCI Common Toxicity Criteria (CTC Version 3.0). Due to delayed toxicities attributable to radiotherapy, all toxicities observed within 1 month after SRT will be scored. DLT is defined as any of following toxicities, that is possibly, probably or definitely related to SRT occurring within 30 days from the start of treatment:

- a) grade 4 or 5 hepatic
- b) grade 4 or 5 gastrointestinal
- c) grade 4 or 5 thrombocytopenia
- d) grade 4 hepatic liver enzyme elevations persisting for  $\geq 5$  days
- e) any adverse event requiring interruption of therapy by  $\geq 2$  weeks (14 calendar days). This does not include patient desire to discontinue therapy. It does include failure for thrombocytopenia to improve to a level of 80 requiring interruption of therapy.
- f) Any grade 5 treatment-related adverse event

The MTD of SRT is defined as the highest dose level at which no greater than 2 DLT is observed in 6 patients.

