#### Dose-escalation Rules

A standard cohort escalation design will be employed to evaluate 3 dose levels of SRT. Three patients will initially be treated at each dose level. A minimum of 1 month of observation after surgery is required in all 3 patients before escalation is initiated.

At the second dose level, 3 patients are entered. If:

0/3 have DLT	then the third dose level is investigated.
2/3 have DLT	then the MTD is exceeded at the second dose level. De-escalation of SRT to the first dose level will be considered.
1/3 have DLT	then 3 additional patients are entered. If none of the additional patients develop DLT, then the third dose will be investigated. Otherwise, the MTD is exceeded at the second dose level. De-escalation of SRT will be considered.

At the third dose level, 3 patients are entered. If:

0/3 have DLT	then the fourth dose level is investigated.
2/3 have DLT	then the MTD is exceeded at the third dose level. The second dose level will be expanded to a total of 6 patients (if only 3 patients had been treated).
1/3 have DLT	then 3 additional patients are entered. If none of the additional patients develop DLT, then the fourth dose will be investigated. Otherwise, the MTD is exceeded at the third dose level.

At the fourth dose level, 3 patients are entered. If:

0-1/3 have DLT	then 3 additional patients are entered. If at most 1 of 6 patients develops DLT, then the fourth dose will be declared the MTD. Otherwise, the MTD is exceeded and the third dose level will be expanded to a total of 6 patients (if only 3 patients had been treated).
2/3 have DLT	then the MTD is exceeded and the third dose level will be expanded to a total of 6 patients (if only 3 patients had been treated).

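### Section 10.1 defines the MTD as up to 2 DLTs in 6, its own escalation table rejects 2 in 6, one level III branch has no next step, and cohort sizes disagree across sections

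*Combined protocol and SAP*

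**What the plan says.** The rules for finding the MTD are spread over several sections.

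- **10.1, Endpoints:** "The MTD of SRT is defined as the highest dose level at which no greater than 2 DLT is observed in 6 patients".
- **10.1, Dose-escalation Rules, levels II and III:** three patients are treated first. After 1/3, three more are added, and the dose goes up only if none of them has a DLT. If any does, level II ends with "Otherwise, the MTD is exceeded at the second dose level" and level III with "Otherwise, the MTD is exceeded at the third dose level".
- **10.1, Dose-escalation Rules, level IV:** "If at most 1 of 6 patients develops DLT, then the fourth dose will be declared the MTD".
- **Lower levels:** after 2/3 at level III, level II is expanded to six if only three were treated there. Both level IV rows do the same for level III. The level III row for 1/3 plus a further DLT has no such step. The table has no row for level I and no acceptance limit for an expanded lower level.
- **9.3:** "SRT dose escalation will be stopped if 2 patients at a given dose level experience a DLT", and "If one patient has a DLT, then an additional five patients will be evaluated at the same dose level".
- **5.2.2:** "The subjects will be divided into groups of 5". The Abstract, the dose table in Section 2.0 and the opening of 10.1 all give 3-6 per level.
- **10.3:** with six evaluable patients, at least a 68% chance of not escalating at a DLT rate of 35% or higher, and a 66% chance of escalating at 20%.
- **10.5:** 18 evaluable patients through level IV, and at most 28 with the ten expansion patients.

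**The concern.** From the same data, two readers could declare different MTDs. Suppose level II shows 0/3 and level III ends at 2/6 (1/3, then one more). The Endpoints sentence makes level III the MTD. The table says level III exceeds the MTD and stops, so no level with six patients remains to be named.

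A 2/6 result does not escalate under either wording, so the climb itself is unaffected. What changes is the dose reported as the MTD (secondary objective 1.2.1) and the dose given to the ten patients in 10.2. For those ten, the one-month observation between groups is dropped. Section 10.2 says DLT monitoring continues as set out in the next section, but 10.3 holds only two escalation probabilities and no stopping boundary.

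The cohort-size conflict affects how many patients are exposed at each level and whether the totals in 10.5 can be met.

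**Working it through.** **Inputs.** The rules are those listed above. p is the true DLT rate and q = 1 - p. The table lists 2/3 but not 3/3; I read 2/3 as two or more.

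**1. Reproduce 10.3.** Fixed six, pass with at most one DLT: P(X ≤ 1 | 6, p) = q^6 + 6pq^5.
- p = 0.20: 0.655 pass (stated 66%).
- p = 0.35: 0.319 pass, so 0.681 do not (stated 68%).

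With at most two of six, the same figures are 0.901 and 0.353. The plan's numbers were therefore computed with the 1-of-6 limit.

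**2. Acceptance of a single level under each limit.**

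- Six-patient level with a stop at 2/3 (level IV). At most 1/6: q^6 + 6pq^5. At most 2/6: P(0/3)·P(≤2/3) + P(1/3)·P(≤1/3).
- Levels II-III as tabled: q^3 + 3pq^2·q^3. Allowing 2/6 adds (3pq^2)^2.
- Lower level expanded after 0/3: P(≤1/3) versus P(≤2/3) in the three added patients.

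| Setting | Limit | p = 20% | p = 35% | p = 50% |
|---|---|---|---|---|
| Six-patient level | ≤1/6 | 65.5% | 31.9% | 10.9% |
| | ≤2/6 | 85.2% | 58.1% | 29.7% |
| Levels II-III sequence | ≤1/6 | 70.9% | 39.6% | 17.2% |
| | ≤2/6 | 85.6% | 59.3% | 31.3% |
| Expanded after 0/3 | ≤1/6 | 89.6% | 71.8% | 50.0% |
| | ≤2/6 | 99.2% | 95.7% | 87.5% |

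The disputed path, 1/3 then 1/3, has probability (3pq^2)^2: 1.8% at p = 5%, 5.9% at 10%, 14.7% at 20% and 19.7% at 35%.

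**3. Open level III branch.** At p = 0.35:
- 1/3 plus a further DLT: 0.4436 × 0.7254 = 0.3218.
- Two or more of the first three: 0.2817.
- Share of level III rejections that fall in the open branch: 0.3218 / 0.6035 = 53%.

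With assumed rates of 20% at level II and 35% at level III, 0/3 at level II followed by this branch has probability 0.512 × 0.3218 = 16.5%. With exactly 2/6 at level III it is 0.512 × 0.1968 = 10.1%.

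**4. Whole trial, exact enumeration under assumed DLT rates for levels I-IV.** Escalation follows the table. When a level is rejected, the level below is accepted if it already stands at 1/6, or expanded to six if it stands at 0/3 and then judged at the limit. The open level III branch is filled in this way. Remaining probability goes to level I. Under the looser limit, a level ending at 2/6 becomes the MTD.

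| Assumed rates | Outcome | ≤1/6 | ≤2/6 everywhere | ≤2/6 only for lower levels expanded after 0/3 |
|---|---|---|---|---|
| 10/20/35/50% | MTD has true rate ≥35% | 23.2% | 41.5% | about 27% |
| 5/10/20/35% | MTD has true rate ≥35% | 20.5% | 37.3% | 20.5% |
| 5/5/10/20% | level IV declared the MTD | 57.8% | 75.2% | 57.8% |

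**5. Cohort sizes against 10.5.**
- Three plus three: 3 levels × 6 = 18, and 18 + 10 = 28, as stated.
- Three plus five (9.3): 3 × 8 = 24, and 34 with the expansion.
- Five plus five (5.2.2 with 9.3): 3 × 10 = 30, and 40.
- Groups of five with a stop at two DLTs and no added patients (an assumed reading): 15, and 25. This escalates 73.7% of the time at p = 20% and 42.8% at 35%.

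Only three plus three gives the stated totals.

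**6. What 10.3 describes.** At levels II-III the table escalates at once after 0/3. From step 2, it escalates with probability 70.9% at a 20% rate and fails to escalate with probability 60.4% at 35%. The 66% and 68% are right for six patients judged together, as at level IV, but are not escalation probabilities for levels II-III.

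**The case against.** The strongest reply is that the table governs. It says in terms that the MTD is exceeded at levels II and III, and it demands at most 1 of 6 at level IV. Section 9.3 agrees. A team following the table would never accept 2/6 at those points, so the 41% and 37% require staff to set aside explicit operating rules. This stands as far as it goes: those figures are upper bounds. With 2/6 allowed only where the table is silent, they become about 27% and 20.5%.

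The assumed rates have no source in the plan, which expects little toxicity and describes a cited liver-metastases trial with no DLT at any level. At a 5% rate the disputed path is rare (1.8%). That limits the size of the problem but does not remove the contradiction, and an escalation trial has to work when the expectation proves wrong.

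The open level III branch has an obvious filler, since the neighbouring rows all expand the level below. A sensible reader would supply it, but the protocol should say it.

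Section 9.3 also lets escalation be halted outside the formal rules and therapy be stopped for unacceptable toxicity. These are real safeguards, but they do not say which dose is the MTD.

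Section 10.3 is conditioned on six evaluable patients and is correct on that condition. That item is minor.

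**Conclusion.** The concern holds and should be fixed before the rules are used. The contradictions are in the current text and do not come from redaction or broken tables. The Endpoints sentence conflicts with three other parts of the plan, and where the table is silent it is the only acceptance rule. There the looser limit raises acceptance of a level with a 35% DLT rate by about 24 percentage points (95.7% less 71.8%).

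The single-level figures are exact given a true DLT rate. The whole-trial figures depend on assumed rates and on how far the sentence is taken to override the table. Under 10/20/35/50%, the chance of declaring an MTD with a true rate of 35% or more rises from 23% by between 4 and 18 points. Under 5/10/20/35%, it rises from 20.5% by between 0 and 17 points. The cohort-size conflict needs no assumption: adding five patients after one DLT can take the trial past its stated maximum of 28.

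**What to change.** 1. **10.1, Endpoints:** define the MTD as the highest level with at most one DLT among six patients, and say that this covers level I and any lower level expanded to six.
2. **10.1, Dose-escalation Rules, level III:** after 1/3 plus a further DLT, expand level II to six if only three were treated there, as the 2/3 row already does. Say the same where level III is expanded after level IV fails and is then itself rejected.
3. **9.3 and 5.2.2:** change the five added patients to three, and the groups of five to cohorts of 3-6.
4. **10.3 (minor):** give about 60% for not escalating at 35% and about 71% for escalating at 20% at levels II-III. If 68% and 66% are kept, label them as the probabilities of rejecting level IV at 35% and of declaring it the MTD at 20%.
5. **10.5 (optional):** keep 18 and 28, and state whether level I opens if levels IV, III and II all fail. That path needs 0/3 followed by two or more of three at both II and III. Its probability is at most 0.0775² = 0.6%, and it would need up to 4 × 6 = 24 patients, or 34 with the expansion.

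**Cost.** This is mostly wording. Item 2 adds three patients at level II in that branch and stays within 18 (six at each of levels III, II and I). Item 4 makes the stated protection look weaker but changes no operating characteristic. The real price, relative to the looser sentence, is more frequent rejection of a level with a 20% DLT rate: 10.4% instead of 0.8% after 0/3, and 34.5% instead of 14.8% for a six-patient level. Under assumed rates of 5/5/10/20%, level IV is declared the MTD in 58% of trials instead of 75%. The escalation table already carries that price wherever it states a limit.

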#### Dose-escalation Rules

A standard cohort escalation design will be employed to evaluate 3 dose levels of SRT. Three patients will initially be treated at each dose level. A minimum of 1 month of observation after surgery is required in all 3 patients before escalation is initiated.

At the second dose level, 3 patients are entered. If:

0/3 have DLT	then the third dose level is investigated.
2/3 have DLT	then the MTD is exceeded at the second dose level. De-escalation of SRT to the first dose level will be considered.
1/3 have DLT	then 3 additional patients are entered. If none of the additional patients develop DLT, then the third dose will be investigated. Otherwise, the MTD is exceeded at the second dose level. De-escalation of SRT will be considered.

At the third dose level, 3 patients are entered. If:

0/3 have DLT	then the fourth dose level is investigated.
2/3 have DLT	then the MTD is exceeded at the third dose level. The second dose level will be expanded to a total of 6 patients (if only 3 patients had been treated).
1/3 have DLT	then 3 additional patients are entered. If none of the additional patients develop DLT, then the fourth dose will be investigated. Otherwise, the MTD is exceeded at the third dose level.

At the fourth dose level, 3 patients are entered. If:

0-1/3 have DLT	then 3 additional patients are entered. If at most 1 of 6 patients develops DLT, then the fourth dose will be declared the MTD. Otherwise, the MTD is exceeded and the third dose level will be expanded to a total of 6 patients (if only 3 patients had been treated).
2/3 have DLT	then the MTD is exceeded and the third dose level will be expanded to a total of 6 patients (if only 3 patients had been treated).

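### In the 10.1 escalation rows a second DLT settles the fate of a dose level, but no sentence closes entry to the unfinished group of patients

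*Combined protocol and SAP*

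**What the plan says.** The Dose-escalation Rules in 10.1 set the first group: "Three patients will initially be treated at each dose level". What follows depends on the number of DLTs.

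- **Level II, one DLT in three:** "then 3 additional patients are entered. If none of the additional patients develop DLT, then the third dose will be investigated"; otherwise the level exceeds the MTD. Level III has the same structure.
- **Level II, two DLTs in three:** "then the MTD is exceeded at the second dose level. De-escalation of SRT to the first dose level will be considered". No second group is entered.
- **Level IV:** a second group of three follows none or one DLT in the first three. "If at most 1 of 6 patients develops DLT, then the fourth dose will be declared the MTD"; otherwise the level is rejected.

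The Data and Safety Monitoring Plan (9.3) adds four statements:

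- **Two DLTs:** "SRT dose escalation will be stopped if 2 patients at a given dose level experience a DLT". Entry at the current level is not mentioned.
- **A single DLT:** 9.3 extends the level by a different number from the table. "If one patient has a DLT, then an additional five patients will be evaluated at the same dose level".
- **Discretionary halt:** where further escalation looks hazardous, then "regardless of whether the formal stopping rules are satisfied, dose escalation will be halted pending a review of all data".
- **General clause, with no count attached:** "Therapy will be discontinued at any time due to the development of unacceptable toxicity".

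Section 9.3 also provides for weekly review by the investigators and a four-week wait between dose levels. The Endpoints part of 10.1 scores DLTs over 30 days from the start of treatment. It defines the MTD as the highest level with no more than two DLTs in six patients.

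**The concern.** Every escalation row treats a second DLT at a level as rejection of that level. The rows, however, are written for complete groups of three and are silent on what happens if the second DLT appears while a group is still filling. The two rules in 9.3 that act on DLTs or on hazard both act on moving up a level, not on patients still due at the current one. The clause on unacceptable toxicity and the weekly review could lead an investigator to stop entry, but neither sets a threshold for doing so. Section 5.6.3 removes only the patient who had the DLT.

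By contrast, 9.3 has an explicit two-patient rule that stops marker implantation itself. For SRT the equivalent rule reaches only escalation.

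At stake is treatment of a small number of patients at a level that the table has already rejected, when their outcomes cannot alter the table's decision. Most of the listed DLTs are grade 4 or 5 events.

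**Working it through.** **Inputs.** Groups of three and the row outcomes come from 10.1; the alternative of five additional patients comes from 9.3. DLT rates of 20% and 35% are those used in 10.3; 50% is an assumption. Three DLTs in three has no row of its own and is treated like two in three. Write p for the true DLT rate and q = 1 − p.

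**The plan's own figures (10.3).** The plan states at least 68% not escalating at 35%, and 66% escalating at 20%. For a fixed six patients with at most one DLT allowed, P(escalate) = q⁶ + 6pq⁵.

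- p = 0.35: 1 − 0.319 = 68.1% not escalating. This matches.
- p = 0.20: 65.5% escalating. This matches.

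The two-stage table gives P(escalate) = q³ + 3pq² × q³, hence 60.4% not escalating at 35% and 70.9% escalating at 20%. Allowing two DLTs in six gives 35.3% and 90.1%. So 10.3 shares the table's limit of one DLT in six, but not its staging.

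**Entries after the second DLT, levels II and III.** Assume patients enter one at a time and each outcome is known before the next entry. There are two routes:

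- The first two patients both have a DLT (probability p²): one patient of the group remains.
- One DLT in the first three (probability 3pq²), then the second DLT falls on patient 4 (probability p, two remain) or on patient 5 (probability qp, one remains).

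Expected number = p² + 3pq²(2p + qp).

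- p = 0.20: 0.04 + 0.384 × 0.56 = 0.255
- p = 0.35: 0.1225 + 0.4436 × 0.9275 = 0.534
- p = 0.50: 0.25 + 0.375 × 1.25 = 0.719

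P(at least one such entry) = p² + 3pq²(p + qp). Dividing by P(level fails) = 1 − P(escalate) gives the chance among failed levels.

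| | p = 0.20 | p = 0.35 | p = 0.50 |
|---|---|---|---|
| P(escalate), table | 70.9% | 39.7% | 17.2% |
| Mean patients, groups completed | 4.15 | 4.33 | 4.13 |
| Mean patients, entry closed at second DLT | 3.90 | 3.80 | 3.41 |
| Expected entries after second DLT | 0.26 | 0.53 | 0.72 |
| P(at least one) | 18% | 38% | 53% |
| P(at least one), given the level fails | 61% | 63% | 64% |

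The maximum is 2 patients per level.

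**Level IV.** A second group also follows 0/3, which adds q³p² to the expected number: 0.28, 0.57 and 0.75.

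**Five additional patients (9.3).** Expected number = p² + 3pq²(4p + 3qp + 2q²p + q³p) = 0.67, 1.22 and 1.40. The maximum is 4.

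**Effect of closing entry.** Enumerating every outcome sequence, the table's decision for the level is the same with and without closure, so P(escalate) is unchanged.

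**Lower end.** If all patients of a group are treated concurrently, none enters after the second DLT is known, and the number is 0.

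**The case against.** The strongest reply is that silence is not an instruction. A reader might infer that the table orders continued entry after two DLTs. It does not: no second group follows two DLTs in three, and the row quoted above is triggered by one DLT, not two. The gap is confined to an unfinished group. That stands, and it limits the size of the point. It does not remove it, because the entry of three patients is the only operative text and no other sentence closes the group.

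A reader might also infer that later patients never affect any decision. That is not supported either, for three reasons.

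- The Endpoints definition accepts two DLTs in six. The path of one DLT in three followed by a total of two in six has probability (3pq²)²: 14.8% at p = 0.20 and 19.7% at p = 0.35. Under that definition such a level could still be the MTD, and the remaining patients would matter.
- A level expanded to six after the next one fails has no decision row, so the table does not say what a second DLT there means.
- De-escalation from level II is only to be considered, so further outcomes could inform that judgement.

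A third inference, that patients would be treated at a dose shown to be over-toxic, also goes too far. Two DLTs are a rule outcome: at a true rate of 20% a level still fails with probability 1 − 0.709 = 29%.

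Finally, 9.3 does more than stop escalation, since it has the general discontinuation clause and weekly review. These are real safeguards, but neither gives a count at which entry to a level closes. The fair description is that its two-DLT and discretionary rules act on escalation only.

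**Conclusion.** The point holds for the escalation rows of 10.1: the second DLT fixes the table's outcome, and no sentence closes entry to the unfinished group. At most 2 further patients per level are affected, or 4 if the extension in 9.3 applies. For levels II and III under the table, the expected number runs from 0 up to 0.26, 0.53 or 0.72 at DLT rates of 20%, 35% and 50%.

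The upper values need one-at-a-time entry with each outcome known first. With a 30-day DLT window and no stagger required within a group, the number in practice would be lower. The result also takes the table as the governing rule; it does not extend to an expanded level or to the Endpoints definition of the MTD. Within those limits this is a cheap improvement, not a flaw that undermines the design.

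**What to change.** First reconcile 9.3 with the Endpoints and Dose-escalation Rules parts of 10.1 on three matters: three or five additional patients after one DLT; at most one or at most two DLTs in six; and the decision for a level expanded to six. Which limits to adopt is for the sponsor. Recalculate 10.3 for the rule then in force.

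Then add to 10.1 wording to this effect: *Entry to a dose level closes once the DLTs already observed there make the outcome for that level certain, that is, certain to be rejected under the rule in this section. Patients who have not started SRT are not treated at that level.* The sentence follows whatever limit is adopted; under the present escalation rows it takes effect at the second DLT.

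The cost is one sentence. Escalation and MTD probabilities do not change, because entry closes only when the outcome is already certain. The downside is slightly fewer patients in the toxicity tables for failed levels. The sentence requires no stagger within a group, so the benefit depends on how entry is spaced.

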## Section 1.0 Objectives

- 1.1 Primary Objective:
  - 1.1.1 The safety of hypofractionated stereotactic radiotherapy in patients with advanced hepatocellular carcinoma.
    - 1.1.1.1 Record SRT related liver, right kidney, small bowel toxicity according CTCAEv3.0
- 1.2 Secondary Objective:
  - 1.2.1 The maximum tolerable SRT dose.
  - 1.2.2 Objective tumor response rate.
    - 1.2.2.1 Report the percentage of tumor size change on CT
    - 1.2.2.2 Report the percentage of intensity change on MRI
    - 1.2.2.3 Report the percentage of change in AFP
  - 1.2.3 The value of 4D CT in liver cancer planning
    - 1.2.3.1 Report extent of liver motion three dimensionally
    - 1.2.3.2 Report the percentage of patients requiring breath gating because of the amplitude of organ motion exceeding 1 cm in any dimension.
  - 1.2.4 The value of breath gating in liver cancer SRT
    - 1.2.4.1 Report the success rate of breath gating
    - 1.2.4.2 Report the percentage of treatment time prolongation secondary to the gating.

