Early studies from the international arena demonstrated that a high probability of local tumor control and a low likelihood of late normal tissue toxicity can be accomplished using focused radiotherapy techniques. More recently, Schefter et al have presented results from a phase I study of stereotactic body radiotherapy for the treatment of liver metastases. The dose was escalated from 36 to 60 Gy delivered in three fractions, with three patients in each dose regimen. Dose-volume constraints were specified such that a minimum of 700 ml of unaffected liver could receive no more than 15 Gy (over three fractions). Additional dosimetric constraints were placed on the total kidney volume (no more than 5 Gy per fraction to no less than 35% of the total volume), and on the spinal cord, stomach, and small intestine (maximum doses of 18 Gy, 30 Gy and 30 Gy respectively). No dose-limiting toxicity was observed at any dose level.

Following the methodology of Schefter et al, one can apply the linear-quadratic formalism for radiation cell killing to “equate” schemes that vary the dose/fraction and number of fractions. This concept of biologically equivalent dose (BED) says that the total effect is given by:

$$(nd) \left\{ 1 + d \frac{\alpha}{\beta} \right\}$$

where n is the # of fractions and d is the dose/fraction. The “alpha-beta ratio” characterizes the radiation response of a particular tissue; a higher value is indicative of a tissue that responds acutely to the effects of radiation. Due to their highly proliferative nature, most tumors fall into this category. Because prolonging the treatment time introduces a sparing (repair) effect in acutely responding tissues, there is significant motivation to deliver radiation in larger fractions over a shorter time.

While the dose-fractionation scheme employed by Schefter et al resulted in no significant morbidity, we propose a slightly more conservative dose escalation study as follows:

Dose Level	# Patients	# Fractions	Dose/fraction	Total Dose	Equivalent dose in 2 Gy/fractions
I	3-6	5	8 Gy	40 Gy	60.0 Gy
II*	3-6	5	10 Gy	50 Gy	83.3 Gy
III	3-6	5	12 Gy	60 Gy	110.0 Gy
IV	3-6	5	14 Gy	70 Gy	140.0 Gy

\*Starting dose level is Dose Level II.

For comparison, the 3 x 12 Gy arm in the Schefter study is equivalent to a total dose of 66 Gy in 2 Gy fractions, while the 3 x 20 Gy arm is equivalent to 150 Gy. All calculations assume an alpha/beta ratio of 10.

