## Section 10.0 Statistical considerations

### 10.1 Trial Design

This phase I trial will determine safety, dose-limiting toxicities (DLT) and maximum tolerable dose (MTD) of SRT for HCC. Although unacceptable toxicity is unlikely, four dose levels (40, 50, 60, 70 Gy in 5 fractions) will be evaluated in a cohort escalation design of 3-6 patients. At the MTD, 10 additional patients will be enrolled to generate pilot data on radiologic response and to evaluate further toxicity. Patients will start at dose level II (50 Gy at 5 fractions).

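### Clearing the top dose level would be declared the MTD although nothing above it is tested, so a lower bound would be reported as a maximum

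*Combined protocol and SAP*

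**What the plan says.** Section 10.1 (Trial Design) sets out the ladder: "four dose levels (40, 50, 60, 70 Gy in 5 fractions) will be evaluated in a cohort escalation design of 3-6 patients". The trial starts at level II. The table in section 2.0 likewise ends at level IV, 70 Gy in 5 fractions.

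Under Dose-escalation Rules, level II or III is left for the next level after 0/3 DLT, or after 1/3 followed by no DLT in three more patients. Level IV is taken to six patients unless two of the first three have a DLT, and then: "If at most 1 of 6 patients develops DLT, then the fourth dose will be declared the MTD".

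Under Endpoints, section 10.1 defines the term itself: "The MTD of SRT is defined as the highest dose level at which no greater than 2 DLT is observed in 6 patients". The definition does not require that a higher level was tested and failed.

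Objective 1.2.1 is "The maximum tolerable SRT dose". Sections 10.1, 10.2 and 10.5 tie the 10-patient expansion to the MTD, and section 10.4 ties the response estimates to it. No section says what is reported if tolerance is not exhausted at level IV.

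**The concern.** When level II or III becomes the MTD, the level above it has exceeded the DLT limit, so the maximum is bracketed. When level IV becomes the MTD, nothing above it has been tried. Six patients with 0 or 1 DLT say something about how high the DLT rate at level IV could be. They say nothing about whether a higher dose would be intolerable. One label therefore covers two different findings: a ceiling that was located, and a ladder that ran out.

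What is at stake is the conclusion on objective 1.2.1. It would be reported as met when the trial has only a lower bound, and the expansion and response results would carry the same label.

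The plan's own rationale makes this a realistic outcome. Section 10.1 opens with "Although unacceptable toxicity is unlikely". Section 2.0 says of the cited phase I liver-metastasis study, which escalated to 3 x 20 Gy (150 Gy in 2 Gy equivalents), "No dose-limiting toxicity was observed at any dose level". It then introduces the present ladder, which ends at 140 Gy equivalent, with "we propose a slightly more conservative dose escalation study as follows".

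**Working it through.** **Inputs.** The rules for levels II, III and IV and the start at level II come from section 10.1. The plan gives no expected DLT rate, so every rate p below is an assumption. The only rates it names are the 20% and 35% used in section 10.3.

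**Step 1: reproduce the plan's figures.** Section 10.3 states at least 68% for not escalating at a DLT rate of 35%, and 66% for escalating at 20%. Both come from the probability of at most 1 DLT in 6, L(p) = (1-p)^6 + 6p(1-p)^5:
- 1 - L(0.35) = 1 - 0.3191 = 68.1%
- L(0.20) = 65.5%

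This is the level IV rule. The written rule for levels II and III is E(p) = (1-p)^3 + 3p(1-p)^2 x (1-p)^3. It gives 1 - E(0.35) = 60.4% and E(0.20) = 70.9%, so section 10.3 does not describe those levels.

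**Step 2: probability that level IV is declared the MTD.** This is E(p at II) x E(p at III) x L(p at IV). Unrounded values are carried through.

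| Assumed DLT rate, equal at all levels | E | L | E x E x L |
|---|---|---|---|
| 5% | 0.9734 | 0.9672 | 91.7% |
| 10% | 0.9061 | 0.8857 | 72.7% |
| 15% | 0.8138 | 0.7765 | 51.4% |
| 20% | 0.7086 | 0.6554 | 32.9% |
| 25% | 0.5999 | 0.5339 | 19.2% |
| 35% | 0.3965 | 0.3191 | 5.0% |

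The probability is one half at a common rate of about 15%. At 20% this is still the most likely single outcome (32.9%, against 29.1% for stopping at level II). At 25% it is not (19.2% against 40.0%).

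**Step 3: rates that rise with dose.**

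| Assumed rates at II/III/IV | Level IV declared MTD | Level IV exceeds the limit |
|---|---|---|
| 2/5/10% | 85.8% | 11.1% |
| 5/10/15% | 68.5% | 19.7% |
| 10/15/20% | 48.3% | 25.4% |
| 10/20/30% | 27.0% | 37.2% |

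For the last row: 0.9061 x 0.7086 x 0.4202 = 27.0%.

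**Step 4: sensitivity to the cohort rule.** Section 9.3 adds five patients after one DLT where section 10.1 adds three. With five at levels II and III, E becomes (1-p)^3 + 3p(1-p)^2 x (1-p)^5. Keeping the level IV rule, the 5%, 10% and 15% results become 89.5%, 67.4% and 44.7%.

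**Step 5: what the level IV data can support.** The one-sided 95% exact upper limit for the DLT rate at level IV is 39% after 0/6 and 58% after 1/6. These limits concern level IV alone. No part of the data bears on a higher dose.

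**The case against.** The plan defines its own term. A level IV with at most 1 DLT in 6 satisfies the definition under Endpoints, so the escalation rule applies that definition and does not breach it. This stands: the documents do not contradict themselves on this point. It does not remove the problem, because the definition is what allows a bracketed maximum and an exhausted ladder to share one name.

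The MTD is a secondary objective, and the four-level cap is disclosed. Section 10.4 also tabulates toxicity by dose level, so a careful reader would see that 70 Gy was the highest dose tried. That limits the harm, but the declared result would still be a maximum.

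The strongest objection concerns frequency. A reader might infer that, on the plan's own premise, declaring an unproven maximum is the likeliest result of the trial. The documents do not support that as a flat statement. The remark that unacceptable toxicity is unlikely carries no number. At the two rates the plan does name, the probability is 32.9% and 5.0%. A constant rate also favours the inference, since the ladder climbs from 83.3 to 140 Gy equivalent between levels II and IV. With assumed rates of 10/20/30%, exceeding the limit at level IV is the likelier result. The claim about frequency must stay conditional on low DLT rates.

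**Conclusion.** The point holds as one of labelling and reporting. If level IV is cleared, the plan would report objective 1.2.1 as answered when the trial has shown only that the limit was met at the highest level evaluated. This follows from the written rule and needs no assumption about DLT rates.

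Its probability does rest on assumptions. It ranges from 91.7% (5% at all levels) to 5.0% (35% at all levels), using the section 10.1 rules. It is the main scenario if DLT rates are low, which is how the plan's remark on toxicity reads. It is not the main scenario if rates exceed about 20% at every level or rise steeply.

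The change should be made. It is not critical: the objective is secondary, and neither patient handling nor any operating probability depends on it.

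**What to change.** - **Section 10.1, Dose-escalation Rules, fourth level:** report the outcome of at most 1 DLT in 6 as *MTD not reached; level IV is the highest level evaluated and met the tolerability limit*.
- **Sections 10.1 (Trial Design), 10.2, 10.4 and 10.5:** where the expansion or the response analysis is tied to the MTD, write *at the MTD, or at the highest evaluated level if the MTD is not reached*. This has to accompany the first change, or the 10-patient expansion would have no trigger when level IV is cleared.
- **Section 10.1, Endpoints:** state that a level is called the MTD only if the next higher level was tested and exceeded the DLT limit. The sponsor must first reconcile that limit. The definition accepts up to 2 DLTs in 6, while the escalation rules treat 2 in 6 as exceeding the MTD. Until this is settled, the added condition would be ambiguous.

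The cost is wording only. No dose, cohort or sample size changes. The downside for the sponsor is a slightly less favourable conclusion if level IV is cleared.
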